5.1.2 Exclusion Criteria

An individual who meets any of the following criteria will be excluded from participation in this study:

1. Current suicidal ideation with a plan and/or intent or a suicide attempt within the past 12 months
2. Previous Woebot use

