6.2 Efficacy Assessments and Procedures

6.2.1 Satisfaction

The Client Satisfaction Questionnaire (CSQ-8)

The CSQ-8 is an 8-item measure used to assess client's satisfaction with treatment on a 4-point scale (1 = "very dissatisfied" to 4 = "very satisfied"). Example questions include, "how would you rate the quality of service you received?" and "did you get the kind of service you wanted?" Total sums range from 8-32, with high scores indicating greater satisfaction with Woebot. The CSQ-8 has been widely disseminated and considered both valid and reliable (α ranges = .83-.93).²

[REDACTED]

[REDACTED]

Safety Assessments

Safety events will be captured through participant spontaneous report, in-app content, and via a self-report assessment of Adverse Events (AE) collected at the Week 2/EOS visit. See Section 8.5 for further detail.

7. Study Stopping Rules

Study procedures will be stopped if the Sponsor-Investigator, in discussion with the SAC and/or IRB as applicable, determines that the number and/or severity of AEs justify putting the study on hold.

The study may resume following the safety review, if the Sponsor-Investigator agrees it is safe to proceed.

The Sponsor-Investigator may initiate study closure at any time, provided there is reasonable cause and sufficient notice is given in advance of the intended termination.

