8.5 Safety Monitoring

8.5.1 Safety Procedures At Screening

Study participants will be asked to self-report on recent suicidal thoughts including current suicidal ideation with plan and/or intent as well as attempts in the past 12 months. Responses are not monitored in real time. Participants who endorse having a current suicidal plan and/or intent or an attempt in the past 12 months will be excluded from the study. Participants will be notified that:

- They may benefit from a level of care beyond the scope of the study and investigational treatment.
- They should call 9-1-1 or go to their local emergency room and reach out to someone they trust and can help them stay safe if they feel they are in crisis or in need of medical attention.
- Will be electronically provided with a list of resources.

Participants who endorse current suicidal ideation with a plan and/or intent will also be notified that a member of the study team will attempt to follow-up with them. Three attempts will be made by the Study PI to contact participants with the third being by email and efforts/resolution will be documented in accordance with the study protocol. The study team will make every effort to follow-up with the participant within 3 business days of the initial report.

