8.5.3 Week 2/EOS Safety Event Self-Report

[figure not shown]
Study participants will be asked to self-report on potential safety events at the Week 2 / EOS timepoint. Questions will explicitly ask about changes since starting the study (about 2 weeks ago) in their (1) mental and/or physical health, (2) any new thoughts about ending their life including new intent/plan/or attempts, and (3) any worsening of symptoms that led to changes in their medical care including medications taken for a psychiatric condition and/or therapy. Information gathered through this survey will be used to inform the need for follow-up, AE/SAE/UADE determination, and resolution.

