9.3 Sample Size Determination

Given that this study is for internal exploratory purposes and is relying on descriptive statistics for analyses, no power analyses were conducted. The N of 165 with a 10% attrition rate was determined based on the necessary N for meaningful internal learning.

10. Statistical Methods

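### As summarized, the Week 2 survey does not directly ask about worsening of suicidal ideation that the entry criteria allow at baseline

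*Combined protocol and SAP*

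**What the plan says.** **Entry.** Section 5.1.2 excludes "Current suicidal ideation with a plan and/or intent or a suicide attempt within the past 12 months". Section 8.5.1 applies the same threshold at screening: "Participants who endorse having a current suicidal plan and/or intent or an attempt in the past 12 months will be excluded from the study". Neither section excludes ideation alone.

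**What screening asks.** Section 8.5.1 opens broadly: "Study participants will be asked to self-report on recent suicidal thoughts including current suicidal ideation with plan and/or intent". Section 5 (Study Population) is narrower. It mentions questions on current ideation with a plan or intent and on attempts in the past 12 months, and nothing on thoughts alone.

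**What Week 2 asks.** Section 8.5.3 lists three topics under one stem. The stem and item 1 read: "Questions will explicitly ask about changes since starting the study (about 2 weeks ago) in their (1) mental and/or physical health". Item 2 is "any new thoughts about ending their life including new intent/plan/or attempts". Item 3 is "any worsening of symptoms that led to changes in their medical care", with psychiatric medication and therapy given as part of that care. The answers feed decisions on follow-up and on AE/SAE/UADE status.

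**Other routes.** The Schedule of Events marks AE/SAE assessment at Week 2 only. Section 8.3 adds spontaneous reports, the Language Detection Protocol (LDP) and review of selected transcripts.

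**The concern.** The qualifier in item 2 suits someone who entered with no suicidal thoughts, but the criteria do not guarantee such a population. A participant admitted with passive or unplanned ideation, whose thoughts then became more frequent or more intense, has nothing new to report under item 2 as described. If no treatment changed, item 3 does not apply either. That leaves item 1, where the participant would have to raise suicidal thoughts in answer to a general question.

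This matters because Week 2 is the only scheduled AE assessment and its answers start the follow-up and classification process. Section 10.4.1 makes the safety of DISC-MVP an exploratory aim, measured by event frequencies, and Section 10.4.2 reports n(%). Section 8.2.2 lists no known adverse device effects for the product, so the trial's own capture is the main source of information. A kind of deterioration that is never asked about by name could be missing from those frequencies, in a group for whom it is especially relevant.

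**Working it through.** No figure in the plan bears on this point. Section 9.3 says "no power analyses were conducted", and the safety analysis is descriptive, so there is nothing to reproduce. The check sets the eligibility wording beside the survey wording.

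Take a participant admitted under Section 5.1.2 with ideation but no plan or intent, and ask which Week 2 item reaches each possible change:

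| Change during the study | Item 1 (health change) | Item 2 (suicidality) | Item 3 (worsening that changed care) |
|---|---|---|---|
| New intent, plan or attempt | in general terms | **asked directly** | only if care changed |
| More frequent or intense thoughts, care changed | in general terms | not named | symptoms in general |
| More frequent or intense thoughts, care unchanged | in general terms | not named | not covered |

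The third row is the gap, and the second row is a milder form of it.

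Next, the routes outside the survey:

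- **Spontaneous report** depends on the participant making contact.
- **The LDP** (Section 8.5.4) works on free text typed into the app. Section 4.3 does not require participants to register or engage.
- **Transcript review** (Section 8.3) covers selected conversations.

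Each can detect worsening ideation, but none puts a question about it to every participant. The three sources visible in Section 10.4.1 are spontaneous report, the Week 2 survey and transcript review. Of these, only the survey asks participants directly.

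Last, the baseline. To read a Week 2 answer as new or worsened, one must know whether thoughts were present at entry. Section 8.5.1 implies that this is asked; Section 5 does not. The two descriptions differ, so the documents leave it open.

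On size, the documents give no share of eligible adults with ideation but no plan or intent. Purely as an assumption, a share of 3% to 10% of the roughly 165 randomized would be 0.03 × 165 = 4.95 to 0.10 × 165 = 16.5, or about 5 to 17 people. That counts participants for whom item 2 fits poorly. It does not count people who worsen, still less worsened people whom every route misses.

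**The case against.** The strongest reply is that the survey is broader than item 2. Its stem asks about change since the start of the study, item 1 covers any change in mental health, and intensified ideation is such a change. The second half of item 2 fits the admitted population well: plan, intent and recent attempts are excluded at entry, so asking about new ones is a direct test of escalation past the entry threshold. The LDP runs for everyone in both arms, transcripts are sampled, and Section 8.5.2 provides an unscheduled visit whenever a safety event is suspected. Section 8.5.3 also lists topics, not item text. The questionnaire, the Safety Management Plan and the text of Section 8.5.5 (Transcript Review) are not available to read.

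Most of this stands, and it rules out three stronger readings that a reader might infer:

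- **That the survey asks only about new thoughts, so any worsening is missed.** Escalation to intent, plan or attempt is asked directly, and other worsening has indirect routes.
- **That the safety frequency will be understated.** The documents support only that it could be.
- **That screening fails to record ideation without plan or intent.** Section 8.5.1 suggests that it may be recorded; the fault is inconsistency with Section 5.

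What the reply does not remove is that the one suicidality-specific topic, as described, leaves out a change that participants admitted under the criteria can have. A general item is a weaker prompt, and the plan's inclusion of a separate suicidality item suggests that a general one was not thought sufficient.

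**Conclusion.** The point holds in a narrow form. Worsening of pre-existing suicidal ideation, short of new intent, plan or attempt, is not directly asked about at the only scheduled AE assessment, although the criteria admit people who could experience it. Such events could be under-captured. How many cannot be derived from the documents; the 5 to 17 above rests wholly on an assumed prevalence and is not an estimate of missed events.

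The conclusion assumes that Section 8.5.3 reflects the survey's actual wording. If the instrument already asks about worsening, the fault lies only in the protocol's description. The satisfaction endpoint and its analysis are unaffected. This is a worthwhile, inexpensive improvement to safety capture, not a flaw that undermines the trial.

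**What to change.** 1. In Section 8.5.3, item 2, insert *or worsening* after *new* where it qualifies thoughts, and keep the part on new intent, plan or attempts as it is. Change the survey item to match. If the survey already asks this, correct Section 8.5.3 instead.
2. Reconcile Section 5 with Section 8.5.1 on what screening asks, so that ideation without plan or intent is recorded at baseline. If the broader description in Section 8.5.1 is what is used, only Section 5 needs to change; otherwise one screening response option is added.

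The cost is a few words in one survey item, possibly one screening response, an IRB submission, and a few more positive answers to review. Eligibility, follow-up procedures, sample size and analysis stay as they are.

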8.5.4 Language Detection Protocol (LDP)

In addition to the onboarding screens re-stating that Woebot is not a crisis service, Woebot has a Language Detection Protocol (LDP), developed by Woebot Health. The LDP is available and operates the same regardless of assigned intervention group. The purpose of the LDP is to detect potentially concerning topics within participant-input free-text and will be enacted for all participants regardless of treatment condition. Upon detection of any concerning topics, LDP initiates a conversation to remind the participant of the application's limitations of services and offer a resource list which includes readily accessible support channels. If a possible mention of concerning topics is detected, the participant is reminded of the limitations of services (which they will have already seen in both the informed consent and well as Woebot's onboarding screens) as well as offered a list of external-to-application resources, specifically contact information, that were thoughtfully curated in consultation with suicide prevention experts. This resource list includes emergency contact phone numbers, and suicide ideation and domestic violence hotline information.

8.6 Safety Assessment Committee (SAC)

The SAC is the formal WH committee charged with responsibility for the review and evaluation of previous as well as accumulating data from clinical studies of WH devices, to assess safety, perform signal confirmation and risk assessment, assess the risk-benefit associated with study continuation, efficacy and other trial conduct issues such as scientific merit, and to develop recommendations so as to ensure safety across studies and minimize risk for subjects. The SAC members will include the following individuals:

1. Independent Medical Safety Expert, who will serve as the SAC Chair;
2. A Clinical Development Lead;
3. a Medical Lead;
4. a Regulatory Lead;
5. a Device Vigilance Lead

Validated, accurate and interpretable data are to be provided to the SAC, as requested. Data files to be used for SAC analyses will undergo established data review/QC procedures to the extent possible and critical fields will be identified. The Sponsor must ensure that data is of sufficient quality to support the performance of safety surveillance and confirm the assessment of causality associated with the event(s), the associated WH application and confirmation of reportability.

The SAC will determine whether any missing data will significantly impact the safety assessment and will direct the necessary actions to address missing data.

8.6.1 Risk and Quality Tolerance Limits

Perceived risks and quality tolerance limits (QTLs) will be identified and documented before the study start.

The Sponsor will review risk control measures periodically to ascertain whether the implemented quality management activities remain effective and relevant. The quality management approach and any important deviations from the predefined QTLs (and remedial actions adopted) will be described in the clinical study report (CSR).

8.7 Quality Control and Quality Assurance

The Sponsor maintains a robust Quality Management System (QMS) that includes all activities involved in quality assurance and quality control per 21 CFR 820, to ensure compliance with written SOPs as well as applicable global/local GCP regulations and ICH Guidelines.

Audits of investigator sites, vendors, and Sponsor systems are performed by auditors, independent from those involved in conducting, monitoring, or performing quality control of the clinical trial. The clinical audit process uses a knowledge/risk-based approach.

Audits are conducted to assess 21 CFR 820 and GCP compliance with global and local regulatory requirements, protocols and internal SOPs and are performed according to specified Sponsor processes.

9. Statistical Analysis

9.1 General Methodology

Descriptive statistics will be reported for study measures for each study arm as well as the total sample. Summary reports will be presented for all time periods independently, as well as for relevant change scores from Baseline to Week-2 EOT. For continuous variables that are normally distributed the mean and standard deviation will be reported, for non-normal data the median and interquartile range (IQR) will be reported. Frequencies and percentages will be reported for categorical variables.

9.2 Analysis Sets

Primary and secondary analyses will be completed on two sets of data - the full intent-to-treat sample of anyone randomized with available survey data, as well as a per-protocol sample (i.e., registered for app, completed all assessment timepoints, no protocol deviations, etc).

9.3 Sample Size Determination

Given that this study is for internal exploratory purposes and is relying on descriptive statistics for analyses, no power analyses were conducted. The N of 165 with a 10% attrition rate was determined based on the necessary N for meaningful internal learning.

10. Statistical Methods

10.1 Primary Endpoint

10.1.1 Aim

To explore satisfaction with the DISC-MVP among a group of adults with or without clinical symptoms.

10.1.2 Hypothesis

Participants in the DISC-MVP arm and the DISC-CON arm will have descriptively similar levels of satisfaction.

10.1.3 Endpoints

User satisfaction will be measured by:

- Client Satisfaction Questionnaire (CSQ-8)

10.1.4 Analysis Plan

Statistical analysis will be descriptive. The total scale score from the CSQ-8 will be summarized continuously for both treatment groups as well as overall.

10.2 Secondary Endpoint

10.2.1 Aim

To explore satisfaction with the DISC-MVP among a group of adults with at least mild baseline symptomatology.

10.2.2 Hypothesis

Participants with mild symptomatology and above in both the DISC-MVP arm and the DISC-CON arm will have descriptively similar levels of satisfaction.

10.2.3 Endpoints

User satisfaction will be measured by:

- CSQ-8

10.2.4 Analysis Plan

[figure not shown]
Statistical analysis will be descriptive. Analyses will be restricted to users in each group that had a score of 5 or above on the PHQ-8 and/or the GAD-7 at baseline. The total scale score from the CSQ-8 will be summarized continuously for both treatment groups as well as overall.

[REDACTED]

[REDACTED]

[REDACTED]

[REDACTED]

10.4 Safety Endpoints

10.4.1 Aims and Endpoints

The relative safety of DISC-MVP against a historical control will be investigated as an exploratory aim and measured through:

- Frequency of AE/SAE/UADEs
 - Spontaneous participant report of safety events that are determined to be an AE/SAE/UADE
 - Direct participant self-report of safety events at the Week 2, end of study, survey that are determined to be an AE/SAE/UADE
 - Number of transcript reviews that detect safety events that are determined to be an AE/SAE/UADE

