Abbreviated Title:	Participant Satisfaction with the BUILD Mobile Application
Sponsor:	Woebot Health
Study Type:	Product learning
Number of Participants:	~165 (150 complete)
Number of Sites:	1
Study Objective:	The overarching goal of this study is to explore satisfaction with a version of Woebot that leverages Large Language Models (LLMs) to recreate core therapeutic experiences. As a benchmark for understanding the relative performance, this LLM MVP of Woebot will be compared against a version of Woebot that does not use LLMs.
Primary Aim and Endpoint:	Aim: To explore user satisfaction with the DISC-MVP Endpoints: Client Satisfaction Questionnaire for both treatment groups.
Secondary Aims and Endpoints:	Aim: To explore user satisfaction with DISC-MVP for users with mild symptomatology or above (PHQ-8 or GAD-7 \geq 5). Endpoint: Client Satisfaction Questionnaire for both treatment groups.
	[REDACTED]

	
Study Design:	Randomized controlled trial
Study Duration:	2 week intervention period
Target Population:	Adults with or without clinical symptoms
Key Inclusion Criteria:	
1. Be 18+ years of age and older (no upper limit)2. Own or have regular access to a smartphone with a recent operating system installed (Android: OS 8.0 or higher, Apple: iOS 13.0 or higher) with reliable Wi-Fi access or sufficient data plan to engage with assigned treatment condition for the duration of the study3. Available and committed to engage with the program and complete assessments for a 2-week duration4. Able to read and write in English5. Participants must have primary residence in the United States
Key Exclusion Criteria:	
1. Current suicidal ideation with a plan and/or intent or a suicide attempt within the past 12 months2. Previous Woebot use
Study Conditions:	DISC-MVP

	DISC-CON
Test Device:	DISC-MVP
Control Device:	DISC-CON
Statistical Methods:	Descriptive statistics will be reported for study measures for each study arm as well as the total sample. Summary reports will be presented for all time periods independently. [REDACTED] [REDACTED] [REDACTED] [REDACTED] [REDACTED]
Protocol Version and Date:	1.1 (8/SEP/2023)
Keywords:	digital mental health intervention, chatbot, conversational agent, relational agent, natural language processing, artificial intelligence

Table of Contents

Schedule of Events	12
1. Introduction	13
1.1 Background	13
1.2 Study Rationale	13

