1.3 Investigational Device

Woebot is an automated relational agent based on researched and scientifically validated psychotherapies, primarily CBT, and accessible via iOS and Android applications.

The Woebot LLM MVP (referred to as MVP moving forward) is a minimal version of Woebot [REDACTED]

[REDACTED] the MVP will be compared against a version of Woebot that contains the same scope of features, but does not use LLMs. For safety, both the MVP and control will use the established Language Detection Protocol (see section 8.5.2 for more details).

2. Objectives

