3.1 Description of Trial Design

This study is a double-blind, randomized controlled trial (RCT) exploring user satisfaction with an augmented version of Woebot and a previous version of Woebot among a sample of adults. Participants who consent and meet study eligibility criteria will be randomized 1:1 into one of the 2 arms. Study participation is up to 4 weeks in total, including a 1 week screening/baseline phase followed by a 2 week active intervention phase, and 1 week to complete the final study survey.

Participants will be recruited and enrolled into the study by Lindus Health . All remaining data collection and study monitoring will be managed through the Citrus decentralized trial platform managed by Lindus Health and by designated Woebot Health study personnel.

Self-report survey assessments will be administered to all participants at Screening/Baseline, Day 3, and Week 2. Members of the study team may contact participants through the Citrus platform via phone/sms and/or email to remind participants to complete study activities.

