3.3.2 Randomization

Randomization into the treatment arms will be 1:1 with no additional stratification by group demographics. The study may over enroll in order to meet 75 completed participants in each treatment arm. Participants will be considered randomized once they complete all of their screening and baseline activities including surveys, their identity has been verified, and eligibility has been confirmed (e.g., checked for duplicate registrations).

[figure not shown]
[figure not shown]

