4.1 Study Conditions

Both treatment conditions will be available through a bespoke study app called the ‘Build’ app and will be made available exclusively for study participants through unique access codes.

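### The exploratory relative-safety aim in 10.4.1 names only an undefined historical control and leaves out the concurrent randomised DISC-CON arm

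*Combined protocol and SAP*

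**What the plan says.** The safety aim in 10.4.1 reads: "The relative safety of DISC-MVP against a historical control will be investigated as an exploratory aim". It lists three routes to an event count: spontaneous report, the Week 2 survey and transcript review. Section 10.4.2 then plans n(%) for each safety endpoint. Its visible text names no comparator and does not split by arm.

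Elsewhere the comparator is the concurrent control arm. The Study Objective in the synopsis says "this LLM MVP of Woebot will be compared against a version of Woebot that does not use LLMs", and the synopsis lists DISC-CON as the control device. Section 1.3 says "the MVP will be compared against a version of Woebot that contains the same scope of features, but does not use LLMs". Section 3.1 describes a double-blind randomised trial of "an augmented version of Woebot and a previous version of Woebot among a sample of adults". Section 3.3.2 says "Randomization into the treatment arms will be 1:1 with no additional stratification by group demographics". The hypotheses in 10.1.2 and 10.2.2 name both arms. Section 9.1 sets a general rule that study measures are described for each arm and in total.

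**The concern.** The trial has a randomised, participant-blinded control arm that differs from DISC-MVP, as far as the public text shows, in the use of LLMs. That arm is the natural reference for whether the LLM version produces more safety events. The one sentence that sets out a relative-safety aim does not name it and points instead to a control that the public text does not describe.

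An analyst working from that text cannot tell which data set to use. If the sentence is followed literally, the report would offer a confounded contrast as its statement on relative safety while data for a randomised contrast sit in the same database. Relative safety is of interest for a first LLM version of the product, even when the aim is exploratory.

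**Working it through.** The point rests on text. The plan gives no AE rate, historical data set or safety margin, so there is no figure of its own to reproduce here.

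**Step 1: is the term defined?** The phrase historical control appears once in the public text, in 10.4.1. No source, period, population, observation length or ascertainment method is attached to it. Two places mention earlier data: the UADE definition in 8.2.1 refers to a summary document on previous studies, and 8.6 has the Safety Assessment Committee review data from previous studies. Neither is linked to the aim in 10.4.1.

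**Step 2: test both readings.**

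- *Literal, an outside reference.* Write each term as the proportion of participants with an event. Then (MVP − HIST) = (MVP − CON) + (CON − HIST). The first term on the right is the randomised contrast. The second is whatever separates this trial's control arm from the historical source, and nothing in the design makes it zero.
- *A label for the older version in the control arm.* Section 3.1 does describe the control as a previous version of Woebot. But that arm is randomised 1:1 and followed over the same period, so it is not a historical control.

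Both readings call for an edit.

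**Step 3: what does DISC-CON share with DISC-MVP that an outside source need not?**

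| Feature | Where stated | DISC-CON |
|---|---|---|
| Eligibility, including exclusion for "Previous Woebot use" | 5.1.1, 5.1.2 | Same |
| Bespoke study app; conditions "will be made available exclusively for study participants through unique access codes" | 4.1 | Same |
| Scope of features | 1.3 | Same |
| AE collection from consent to end of study | 8.3.1 | Same |
| Surveys: "Self-report survey assessments will be administered to all participants at Screening/Baseline, Day 3, and Week 2" | 3.1 | Same |
| Week 2 safety questions | 8.5.3 | No restriction by arm |
| Language Detection Protocol | 8.5.4 | Same |
| Participants blinded to arm | 3.3.3 | Same |
| Transcript review | 8.3, 10.4.1 | Allocation by arm not shown |

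The last row matters. Section 8.3 says that only selected conversations are reviewed, and the public text does not show how they are chosen in each arm.

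**Step 4: does the change affect the sample size?** No. Section 9.3 states that no power analysis was done. About 165/2 = 82.5, say 82 per arm, are randomised already.

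**Step 5: how precise would the randomised contrast be?** Event counts are assumed, because the documents give none.

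- With 0 events among 82, the upper limit of the exact two-sided 95% interval for one arm is 1 − 0.025^(1/82) = 4.4%.
- For equal counts in both arms, the Newcombe 95% interval for the risk difference has a half-width of 4.5 points at 0 events per arm and 9.6 points at 8 events per arm.

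The contrast can therefore only be descriptive, which fits the exploratory label.

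**The case against.** The strongest reply is that an external safety reference may be deliberate. The comparator statements in the synopsis, 1.3 and 3.1 concern satisfaction or general performance, not safety. A randomised control for satisfaction and an outside reference for rare events can coexist, and the intervals above show why someone might want more data than 82 per arm provide. This stands in part. A reader might infer that the protocol contradicts itself, but the public text shows an undefined term and an omission, not a proven contradiction.

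Second, redacted text may define the control. There is redaction in the synopsis, the contents list, 1.3 just before the comparator is described, 8.1.1, the text between 10.2.4 and 10.4, and 10.4.2. This stands, and it limits the point to the public text. A hidden definition would still not explain why the visible sentence leaves out the randomised arm.

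Third, 9.1 probably yields AE counts by arm already. This also stands, and it reduces the impact. A reader might infer that the control arm's safety data will go unused, and the documents do not support that. But 9.1 is a general rule for study measures, while 10.4.1 is specific and names a different comparator. Sections 10.1.4, 10.2.4 and 10.5 repeat the split by arm; the visible text of 10.4.2 does not.

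Two further inferences should be resisted. One is a numerical bias obtained by setting a two-week risk in this trial against a longer historical window. AE collection starts at consent, and the schedule allows Day −6 to Day 14 (+6), that is 20 − (−6) = about 26 days. The trial's own window is therefore not a fixed two weeks, and the documents give neither an AE rate nor a historical window. The other is that AE ascertainment is identical in both arms, which transcript review leaves unverified.

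**Conclusion.** The point holds for the public text: 10.4.1 states relative safety only against an undefined historical control and omits the concurrent randomised arm. Either reading of the term needs correction. The size of any bias is unknown. The practical impact is minor, because the aim is exploratory and descriptive, no test or sample size depends on it, the CSQ-8 results are untouched, and by-arm AE counts are probably produced anyway. It is still worth fixing, because a literal analysis would put a confounded contrast where a randomised one is available at almost no cost. The conclusion assumes that no redacted passage already makes DISC-CON the safety comparator.

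**What to change.** In 10.4.1, name the concurrently randomised DISC-CON arm as the comparator for relative safety. In 10.4.2, state that n(%) of participants with an AE, SAE or UADE is reported by arm and overall, in line with 9.1.

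If an external reference is also intended, keep it as a labelled supplement and name its source, population, period, observation length and method of AE ascertainment. A descriptive risk difference with a 95% interval, and no test, is optional.

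The cost is one phrase in 10.4.1 and one sentence in 10.4.2, plus a short description if an external reference is kept. The DISC-CON comparison needs no new data and no change in N, and probably no new table.
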